6.11. Health Outcomes Analyses

All health outcome measures will be analyzed or summarized for SP III, SP III/IV, and SP III/IV/V, if appropriate.

For MSQ (total score and 3 domain scores), MIDAS (total score and item scores), MIBS-4 (total score), PHQ-9 (overall score), and GAD-7 (total score),

- when there are repeated measures, they will be evaluated using MMRM as described in Section 6.1.
- when there is single post-baseline measure, they will be evaluated using ANCOVA model as described in Section 6.1.

PHQ-9 binary indicator of MDD and GAD-7 binary indicator of anxiety will be analyzed using GLIMMIX method as described in Section 6.1.

For PHQ-9 overall level of depression severity and GAD-7 overall level of anxiety severity, as the severity categories do not follow normal distribution, the change from baseline score will be analyzed using nonparametric tests: Kruskal–Wallis test (Kruskal and Wallis 1952) for treatment comparison, and Wilcoxon Signed-rank test (Wilcoxon 1945) to compare the change from baseline within each treatment group.

Individual item scores of these health outcome questionnaire may be summarized if deemed necessary.

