5.3. Method of Assignment to Treatment

Following a prospective baseline (30 to 40 days) period, eligible patients will be randomized in a 1:1 ratio to receive placebo or 120 mg/month of galcanezumab (with a 240 mg loading dose at the first injection [administered as 2 injections of 120 mg at Visit 3]), respectively, and will begin a 3-month double-blind treatment phase. Patients who complete the double-blind period may enter a 3-month open-label extension phase during which all patients will receive galcanezumab 120 mg/month. At Visit 7, patients originally assigned to placebo will receive an initial loading dose of 240 mg galcanezumab; patients originally assigned to galcanezumab will continue the dose of 120 mg but will receive 2 injections (1 injection of 120 mg galcanezumab and 1 injection of placebo) to maintain blinding. At Visit 8 and Visit 9 of the open-label phase, all patients will receive a 120 mg dose of galcanezumab. All patients will be followed for a 4-month, post-treatment phase during which no study medication will be administered.

Patients who meet all criteria for enrollment will be randomized to double-blind treatment at Visit 3. Assignment to treatment groups will be determined by a computer-generated random sequence using an interactive web-response system (IWRS). The IWRS will be used to assign double-blind investigational product to each patient. Site personnel will confirm that they have located the correctly assigned package by entering the confirmation number found on the package into the IWRS.

To achieve between-group comparability, the randomization will be stratified by country and baseline migraine frequency (<8 MHDs versus \geq 8 MHDs). To ensure an appropriate balance of patients with low- and high-frequency MHDs, the sponsor will stop enrollment of low-frequency patients if the number exceeds an estimated 292.

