For continuous variables with repeated measures, change from baseline will be analyzed using a mixed model repeated measures (MMRM) analysis. An MMRM analysis refers to a restricted maximum likelihood (REML)-based, mixed-effects repeated measures analysis using all the longitudinal observations at each post-baseline visit.

For other continuous variables, the change from baseline to last-observation-carry-forward (LOCF) endpoint will be analyzed using an analysis of covariance (ANCOVA) model.

Unless otherwise specified, when ANCOVA model is used to analyze a continuous efficacy variable, type III sum-of-squares for the LSMMeans will be used for the statistical comparisons.

Binary variables with repeated measures will be analyzed in a generalized linear mixed models (GLIMMIX) as pseudo-likelihood-based mixed effects repeated measures analysis.

For categorical efficacy variables without repeated measures, comparisons between treatment groups will be performed using logistic regression model. For other categorical variables without repeated measures, comparisons between treatment groups will be performed using the Fisher's exact test. Unless specified otherwise, Fisher's exact test will be used for comparisons of categorical safety measures; logistic regression will be used for comparisons of post-baseline efficacy measures.

[Table CGAX. 6.1](#) describes the rules for determining the patient population and baseline and postbaseline observations for each study phase and type of analysis. When "last of Visit x-x" is used in the table, the last non-missing observation obtained in the visit interval will be used.

Any change to the data analysis methods described in the protocol will require an amendment ONLY if it changes a principal feature of the protocol. Any other change to the data analysis methods described in the protocol, and the justification for making the change, will be described in the clinical study report or SAP. Changes may only be made in the SAP prior to unblinding.

Additional exploratory analyses of the data will be conducted as deemed appropriate.

Statistical analysis of this study will be the responsibility of Eli Lilly and Company or designee. SAS® software will be used to perform most or all statistical analyses.

Table CGAX. 6.1 Patient Population with Baseline and Postbaseline Definitions by Study Period and Type of Analysis

Study Period/Analysis	Patient Population	Baseline Observation	Postbaseline Observation(s)

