6.2. Adjustments for Covariates

The MMRM models will include the fixed, categorical effects of treatment, country, month, and treatment-by-month interaction, as well as the continuous, fixed covariates of baseline value and baseline-by-month interaction. The baseline value and baseline-by-month interaction are included to account for the differential influence over time that the baseline value has on the post-baseline values. Country will be excluded from MMRM models for safety measures.

When an ANCOVA model is used to analyze a continuous efficacy at the LOCF endpoint, the model will contain the main effects of treatment, country, and appropriate baseline value as a covariate. When an ANCOVA model is used to analyze a continuous safety variable, the country will be removed from the model.

The GLIMMIX models for the repeated binary outcomes will include the fixed, categorical effects of treatment, month, and treatment-by-month interaction, as well as the continuous, fixed covariate of baseline value. Country and the baseline value-by-month interaction will be excluded from the model in order to increase the likelihood of convergence.

When a logistic regression is used to analyze a binary variable, the model will include the main effect of treatment, country (if appropriate), and appropriate baseline value as a covariate. Country may be excluded from the model in case of non-convergence.

With the exception of efficacy analyses on migraine headache days or categorical analysis of response rate (such as 50% response rate) derived from migraine headache days where the continuous value of baseline migraine headache days will be used as covariate, all other efficacy analyses will include baseline number of migraine headache days category (<8 vs ≥ 8) as a covariate in the MMRM, ANCOVA, GLIMMIX and logistic regression model. Specifically, for time to event analysis of 50% response (such as Time to first 50% response in double-blind treatment phase and Time to first loss of 50% response in post-treatment phase), stratified log rank test will be used with the baseline number of migraine headache days category (<8 vs ≥ 8) as one of the covariates.

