If statistically significant improvement is observed at Month 1 and maintained for all the subsequent months during the double-blind treatment phase for the number of monthly migraine headache days, the number of weekly migraine headache days in Month 1 will be analyzed to identify the earliest week where the statistically significant improvement is observed and maintained for all the subsequent weeks in Month 1 for patients who have a monthly diary compliance rate greater than 50% for Month 1.

The number of weekly migraine headache days in Month 1 can be considered as ordinal data with possible values of 0, 1, 2, 3, 4, etc. and will be analyzed using an ordinal repeated measures model using the GLIMMIX procedure in SAS. In this model, a proportional odds model with cumulative logit link will be used, and a random intercept will be applied to the observations for each patient to account for repeated measures. The model will include the fixed, categorical effects of treatment, country, week, and treatment-by-week interaction, as well as the continuous, fixed covariate of weekly baseline number of migraine headache days and weekly baseline number of migraine headache days-by-week interaction. Log (number of compliant calendar days within each week/7) will be included as the offset in the model. For weekly diary compliance rate $\leq 50\%$, the number of weekly migraine headache days during that week will be considered missing.

The weekly baseline number of migraine headache days will be derived as (the monthly number of migraine headache days)/30*7.

Time to Event Measures

For the following time to event measures, a Kaplan-Meier curve of the time to event and treatment group comparison using stratified log-rank test stratifying for country, baseline MHD frequency category will be provided.

- Time to first 50% response in SP III for ITT population.
- Time to first loss of 50% response in SP V for patients who met 50% response criteria at their last injection interval and also entered SP V.

- Time to initiation of preventative treatment for migraine or probable migraine in SP V for patients who entered SP V and those who are not on concurrent preventive treatment group.

Distribution of Response Rate

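### SAP 6.11 compares the PHQ-9 and GAD-7 severity levels by Kruskal-Wallis on change from baseline without conditioning on baseline level, which loses power on a supplementary tertiary analysis

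*SAP*

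**What the plan says.** SAP 6.11 plans three kinds of analysis for these scales.

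- **Total scores.** MMRM where there are repeated measures, ANCOVA where there is one post-baseline measure. In the double-blind phase the Schedule of Activities collects both scales only at Visits 3 and 7, so ANCOVA applies. For an efficacy ANCOVA, SAP 6.2 states that "the model will contain the main effects of treatment, country, and appropriate baseline value as a covariate".
- **Binary indicators.** GLIMMIX.
- **Severity levels.** The sentence opens "For PHQ-9 overall level of depression severity and GAD-7 overall level of anxiety severity", gives non-normality of the categories as the reason, and continues that "the change from baseline score will be analyzed using nonparametric tests". It names the "Kruskal–Wallis test (Kruskal and Wallis 1952) for treatment comparison" and a signed-rank test within each arm. No covariate or stratum is mentioned.

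SAP 5.4.3.4 and 5.4.3.5 define five PHQ-9 levels and four GAD-7 levels. Protocol Table CGAX.2 places change to Month 3 on both scales under a tertiary objective. Protocol 10.3.7.1 adds only that categorical measures will also be analysed.

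**The concern.** Non-normality is a good reason to use a rank or ordinal method. It is not a reason to give up conditioning on baseline. A test on the difference between two levels has three weaknesses that a test of the Month 3 level within baseline level avoids.

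- It carries the baseline noise into the outcome. Unless the correlation is perfect, the difference is noisier than the baseline-adjusted outcome.
- It ranks all one-level moves as equal, so minimal to mild counts the same as moderate to moderately severe.
- It pools zeros of different kinds. A patient who starts at minimal cannot improve, and that zero is tied with the zero of a patient who could have improved and did not.

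What is at stake is power for one supplementary view of depression and anxiety symptoms. A shift in severity level could go undetected in this table, or the level analysis could disagree with the total-score analysis of the same scale partly because only one of them adjusts for baseline.

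**Working it through.** **1. The plan's own figure.** Inputs from Protocol 10.1 and SAP 5.2: effect size 0.33, two-sided alpha 0.05, power 90%, discontinuation 20%. The two-sample t-test needs 193.9, so 194 evaluable patients per arm. 194/0.8 = 242.5, so 243 per arm and 486 in total, as stated. Power at 194 per arm is 0.900. Completers are 2 × 243 × 0.8 = 388.8, against the Protocol's 388. This applies to the primary endpoint only; no power is stated for PHQ-9 or GAD-7. The checks below use 194 per arm.

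**2. Why a change score loses.** With equal variances at the two times and correlation ρ, the change has variance 2(1 − ρ) and the baseline-adjusted outcome has 1 − ρ². The ratio is 2(1 − ρ)/(1 − ρ²) = 2/(1 + ρ):

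- ρ = 0.3: 2/1.3 = 1.54
- ρ = 0.5: 2/1.5 = 1.33
- ρ = 0.7: 2/1.7 = 1.18

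It exceeds 1 for every ρ below 1.

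**3. Simulated power on ordinal levels.** Assumed, because the documents give none of it: a latent shift of 0.33 SD at Month 3, ρ from 0.3 to 0.7, and several baseline distributions. With two arms, Kruskal-Wallis is the Wilcoxon rank-sum test. Within a baseline level, ranking the change and ranking the Month 3 level give the same order, so van Elteren by baseline level is the same test on either.

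The first three rows cut normal PHQ-9 scores, clipped to 0–27, at the SAP's levels (1,500 runs each). The last two use five levels with a fixed share in the lowest (2,000 runs each). Entries are power (%) for Kruskal-Wallis on change / van Elteren by baseline level.

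| Assumed baseline | ρ = 0.3 | ρ = 0.5 | ρ = 0.7 |
|---|---|---|---|
| Mean 4, SD 4 | 55 / 78 | 65 / 83 | 78 / 90 |
| Mean 6, SD 5 | 63 / 85 | 75 / 90 | 88 / 96 |
| Mean 9, SD 5 | 67 / 87 | 80 / 92 | 93 / 97 |
| 60% in lowest level | 50.7 / 75.2 | 57.8 / 80.4 | 76.8 / 89.4 |
| 35% in lowest level | 62.2 / 84.0 | 74.6 / 89.3 | 89.8 / 95.8 |

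The smallest gap is 97 − 93 = 4 points and the largest is 75.2 − 50.7 = 24.5. With no effect and ρ = 0.5, rejection was 4.6% to 5.2% across all tests in the second set. In the first set it was 6% for both tests, within simulation error of 5% at 1,500 runs.

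**4. Smaller effects.** The gain shrinks with the effect. One set of runs, with PHQ-9 and GAD-7 cut-offs, gave 1 to 5 points at 0.1, 6 to 8 at 0.15 and 10 to 14 at 0.2. Another gave about 4 to 12 at 0.15.

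**5. The randomization strata.** In the second set the strata were given a weak assumed association with the score. Adding country and MHD category to a rank ANCOVA on baseline level moved power by at most 0.8 points (75.0 to 75.8). Stratifying the change score by the randomization strata alone gained nothing (for example 57.8 against 58.0, and 74.6 against 73.3).

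**6. The total score.** At an effect of 0.33, mean/SD 4/4 and 6/5, and ρ of 0.5 and 0.7, baseline-adjusted ANCOVA on the total score had 94% to 100% power. Van Elteren on the level had 81% to 95%.

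**The case against.** The best defence is that the endpoint is already well served. Its main analysis is the total score by baseline-adjusted ANCOVA, which is more powerful than either test of the level. The level is a coarsened view, outside the gatekeeping sequence of SAP 6.4, unpowered, and tested with a valid type I error. All of that stands, and it limits the point to a minor one.

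Other parts of the defence also hold. The effect of 0.33 is borrowed from the primary endpoint, and nothing in the documents supports it for these scales. SAP 6.11 defines no level codes, so change in level is the natural reading but still an inference. The floor belongs to the outcome: patients at minimal cannot improve under van Elteren either, although they are then compared only with each other. Exclusion [25] removes serious mood and anxiety disorders but admits stable major depressive and generalized anxiety disorder, so the share starting at the floor is unknown.

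Three stronger readings are tempting and are not supported.

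- **That ignoring the strata costs power.** SAP 5.3 says that "the randomization will be stratified by country and baseline migraine frequency", and the test uses neither factor. The simulated cost is 1 point or less; the loss comes from not conditioning on baseline level.
- **That the test breaches SAP 6.2.** That section says "all other efficacy analyses will include baseline number of migraine headache days category", but ties this to MMRM, ANCOVA, GLIMMIX and logistic models. It also exempts MHD analyses and MHD-based response, which use continuous baseline MHDs. A rank test falls outside the rule.
- **That this is the only unadjusted comparison.** It is the only one among health-outcome and efficacy comparisons with a named method; even the time-to-event measures get a "stratified log-rank test stratifying for country, baseline MHD frequency category". But SAP 5.4.3.3 also promises an analysis of the MIBS-4 burden level, and no test is named for it. SAP 6.1 could send that to an unadjusted Fisher's exact test.

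**Conclusion.** The point holds as a modest loss of efficiency. The planned comparison of severity levels uses baseline only by subtraction and is less powerful than a test that conditions on baseline level. The loss is about 4 to 25 percentage points at an assumed effect of 0.33 and about 4 to 12 points at 0.15, with 194 per arm, correlation 0.3 to 0.7 and the assumed distributions shown. The direction follows from 2/(1 + ρ) for roughly normal scores and was the same in every ordinal scenario simulated at 0.33. The size depends on inputs that the documents do not give.

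A reader might infer that a real effect on depression or anxiety would be missed. The documents do not support that, because the adjusted total-score analysis is planned and is the stronger one. A reader might also attribute any disagreement between the level and total-score results to the missing adjustment, but categorising can cause that too: a PHQ-9 fall from 9 to 5 stays within mild, while 5 to 4 crosses a level. No conclusion on the primary or key secondary endpoints is affected.

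**What to change.** In SAP 6.11, replace the between-arm Kruskal-Wallis test on change with one of these:

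- a van Elteren (stratified Wilcoxon) test of the Month 3 severity level, stratified by baseline level; or
- a proportional-odds model of the Month 3 level with treatment and baseline level. Country and MHD category (<8 versus ≥8) may be added for consistency with SAP 6.2, but not for power.

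Show the baseline-by-Month-3 shift table by arm. State that the total-score ANCOVA is the main analysis of each scale and that the level analysis supports it.

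The cost is one sentence and a standard procedure; the baseline levels are already collected at Visit 3. Sparse upper levels may need collapsing, by a rule set in advance. The proportional-odds version adds an assumption that the van Elteren test avoids. SAP 6.1 allows changes to the SAP only before unblinding; after that, the adjusted test could only be reported as an added analysis beside the planned one.

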6.12. Pharmacokinetic Analyses

Pharmacokinetic assessment will be summarized in the pharmacokinetic/pharmacodynamic (PK/PD) SAP.

6.13. Evaluation of Immunogenicity

To evaluate the changes in immunogenicity data (Anti-LY2951742 [ADA and NAb]) after treatment, the following statistical analyses are planned for comparison between treatment groups:

- The incidence of ADA positive during baseline will be summarized.
- The incidence of treatment-emergent ADA (TE ADA) between treatment groups will be summarized and compared for SP III. The incidence of TE ADA for galcanezumab-treated patients during galcanezumab treatment and the incidence of TE ADA for galcanezumab-treated patients during galcanezumab treatment and post-treatment phase combined will be summarized. This analysis will be done for each immunogenicity analyte (ADA and NAb). The baseline and postbaseline definitions for each Study Period is shown in [Table CGAX. 6.1](#). Treatment-emergent ADA will be defined as any of the following:
 - a negative baseline result and a positive postbaseline ADA result with a titer ≥ 20 . This is also called treatment-induced ADA.
 - a positive baseline result and a positive postbaseline ADA result with a ≥ 4 -fold increase in titers (for example, baseline titer of 10 increasing to ≥ 40 postbaseline). This is called treatment-boosted ADA.
- The incidence of TE ADA and NAb Positive combined between treatment groups will be summarized for the same time periods as planned for the incidence of TE ADA.

The following will also be provided:

- Listing of subjects with TE ADA at any time during study, NAb Status will also be displayed.

- Listing of subjects with TE hypersensitivity reactions or TEAEs related to injection sites for subjects with ADA present at any time.

6.14. Safety Analyses

6.14.1. Extent of Exposure

Patients will receive the investigational medicinal product (IMP) at the following planned time points:

- Beginning of Month 1 (Visit 3)
- Beginning of each month from Month 2 to Month 6 (Visit 5 to Visit 9)

The following information will be recorded on the eCRF for each dose:

- Confirmation that the patient received the IMP (including reason if the IMP was not given)
- Date and time of administration

The following will be derived from the information recorded on the eCRF:

- For treatment phase (SP III), duration of exposure in days is calculated as treatment phase disposition date – first date IMP administered +1.
- For open label phase (SP IV), duration of exposure in days is calculated as open label disposition date - first date IMP administered during SP IV +1.
- For SP III and SP IV separately, number and percentage of patients with 1 dose, 2 doses, and 3 doses injected.
- For galcanezumab-treated time, number and percentage of patients with 1 dose, 2 doses, 3 doses, 4 doses, 5 doses, and 6 doses injected.

6.14.2. Adverse Events

Treatment-emergent adverse events are defined as the reported AEs that first occurred or worsened during the post-baseline phase compared with baseline phase. For each TEAE, the severity level of the event (mild, moderate, or severe) will be determined by patient or physician opinion. The Medical Dictionary for Regulatory Activities (MedDRA) Lowest Level Term will be used in the treatment-emergent computation. For each Lowest Level Term, the maximum severity at baseline will be used as the baseline severity. If the maximum severity during post-baseline is greater than the maximum baseline severity, the event is considered to be treatment-emergent for the specific post-baseline period.

Unless specified otherwise, adverse events will be summarized as follows:

- Treatment-emergent adverse events (TEAEs)

- By preferred term (PT)
- By PT nested within system organ class (SOC)
- By maximum severity
- By considered to be related to study treatment by investigator
- Serious adverse events (SAEs) by PT
- AEs leading to treatment discontinuation by PT

For each patient and TEAE, the maximum severity for the MedDRA level being displayed is the maximum post-baseline severity observed from all associated Lowest Level Terms mapping to the MedDRA level.

For events that are gender specific, the denominator and computation of the percentage will include only patients from the given gender.

6.14.2.1. Safety Topics of Interest

6.14.2.1.1. Potential Hypersensitivity Events

Potential hypersensitivity events (immediate and non-immediate) will be identified from a search of preferred terms generated from the following queries:

- Anaphylactic reaction (SMQ 20000021)
- Broad and narrow terms in the Angioedema (SMQ 20000024)
- Broad and narrow terms in the Hypersensitivity (SMQ 20000214)

A listing of patients having an event identified from these analyses will be reviewed by medical to determine if the terms identified likely represent hypersensitivity events. Listings for the medical review should include information on timing of event relative to latest dose of study drug administration, the event term from this query, other AEs for the patient and timing, any abnormal laboratory findings, and medical history. Events that are judged not hypersensitivity-related will be excluded from the final tables, unless otherwise stated.

The number and percentage of patients with TEAEs, SAEs, and AEs resulting in study drug discontinuation will be summarized by treatment groups using MedDRA PT nested within the SMQ. Events will be ordered by decreasing frequency within the SMQ.

The number and percentage of patients with treatment-emergent (TE) hypersensitivity events by maximum severity will be summarized by treatment groups using MedDRA PT.

